**Table 4 Recommended Cobimetinib Dose Modifications**

Grade (NCI CTCAE v4.0)	Recommended Cobimetinib Dose
Grade 1 or Grade 2 (tolerable)	No dose reduction. Maintain cobimetinib at the same dose of 60 mg QD (3 tablets).
Grade 2 (intolerable) or Grade 3 or 4 (any)	
First appearance	Interrupt treatment until Grade $\leq$ 1, restart treatment at 40 mg QD (2 tablets).
Second appearance	Interrupt treatment until Grade $\leq$ 1, restart treatment at 20 mg QD (1 tablet).
Third appearance	Consider permanent discontinuation.

NCI CTCAE v4.0=National Cancer Institute Common Terminology Criteria for Adverse Events, Version 4.0; QD=once a day.

*Note: Cobimetinib dose re-escalation is permitted on a case-by-case basis after discussion with the Medical Monitor or  designee.*

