**Table 5 Guidelines for Management of Patients Who Experience Specific Adverse Events (Cobimetinib and Atezolizumab) (cont.)**

Event	Action to Be Taken
Hemorrhage	
Grade 3 hemorrhage	
 
• Interrupt cobimetinib treatment. There are no data on the effectiveness of cobimetinib dose modification for hemorrhage events. Clinical judgment should be applied when considering restarting cobimetinib treatment.
 
• Continue atezolizumab treatment.
 

Grade 4 hemorrhage or any grade cerebral hemorrhage	
 
• Interrupt cobimetinib treatment. Permanently discontinue cobimetinib for hemorrhage events attributed to cobimetinib.
 
• Continue atezolizumab treatment.
 

Grade 3 or 4 or intolerable Grade 2 treatment-related toxicities not described above and in Table 4 (dose modifications for cobimetinib)	
 
• Withhold all study treatment.
 
• If event resolves to Grade 1 or better within 12 weeks, resume atezolizumab at fixed dose. If not, permanently discontinue atezolizumab. a, b, c
 
• If event resolves to Grade 1 or better within 28 days, resume cobimetinib with dose reduced by one level. If not, permanently discontinue cobimetinib.
 

a If corticosteroids have been initiated, they must be tapered over  $\geq 1$  month to  $\leq 10$  mg/day oral prednisone or equivalent before atezolizumab can be resumed.

b Atezolizumab may be withheld for a period of time beyond 12 weeks to allow for corticosteroids to be reduced to  $\leq 10$  mg/day oral prednisone or equivalent. The acceptable length of the extended period of time must be agreed upon by the investigator and the Medical Monitor.

c Resumption of atezolizumab may be considered in patients who are deriving benefit and have fully recovered from the immune-related event. Patients can be rechallenged with atezolizumab only after approval has been documented by both the investigator (or an appropriate delegate) and the Medical Monitor.

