**Table 1 Management Guidelines for Endocrine Events**

Event	Management
Asymptomatic hypothyroidism	
 
• Continue atezolizumab.
 
• Initiate treatment with thyroid replacement hormone.
 
• Monitor TSH weekly.
 

Symptomatic hypothyroidism	
 
• Withhold atezolizumab.
 
• Initiate treatment with thyroid replacement hormone.
 
• Monitor TSH weekly.
 
• Consider patient referral to endocrinologist.
 
• Resume atezolizumab when symptoms are controlled and thyroid function is improving.
 

Asymptomatic hyperthyroidism	
TSH <math>\geq</math> 0.1 mU/L and <math><</math> 0.5 mU/L:
 
 
• Continue atezolizumab.
 
• Monitor TSH every 4 weeks.
 
 
TSH <math><</math> 0.1 mU/L:
 
 
• Follow guidelines for symptomatic hyperthyroidism.
 

Symptomatic hyperthyroidism	
 
• Withhold atezolizumab.
 
• Initiate treatment with anti-thyroid drug such as methimazole or carbimazole as needed.
 
• Consider patient referral to endocrinologist.
 
• Resume atezolizumab when symptoms are controlled and thyroid function is improving.
 
• Permanently discontinue atezolizumab and contact Medical Monitor for life-threatening immune-related hyperthyroidism. c
 

MRI=magnetic resonance imaging; TSH=thyroid-stimulating hormone.

a Atezolizumab may be withheld for a longer period of time (i.e., > 12 weeks after event onset) to allow for corticosteroids (if initiated) to be reduced to  $\leq$  10 mg/day oral prednisone or equivalent. The acceptable length of the extended period of time must be agreed upon by the investigator and the Medical Monitor.

b If corticosteroids have been initiated, they must be tapered over  $\geq$  1 month to  $\leq$  10 mg/day oral prednisone or equivalent before atezolizumab can be resumed.

c Resumption of atezolizumab may be considered in patients who are deriving benefit and have fully recovered from the immune-related event. Patients can be re-challenged with atezolizumab only after approval has been documented by both the investigator (or an appropriate delegate) and the Medical Monitor.

## Appendix 8

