### Risks Associated with Atezolizumab and Guidelines for Management of Adverse Events Associated with Atezolizumab (cont.)

**Table 1 Management Guidelines for Endocrine Events (cont.)**

Event	Management
Hypophysitis (pan-hypopituitarism), Grade 2 or 3	
 
• Withhold atezolizumab for up to 12 weeks after event onset.a
 
• Refer patient to endocrinologist.
 
• Perform brain MRI (pituitary protocol).
 
• Initiate treatment with 1–2 mg/kg/day IV methylprednisolone or equivalent and convert to 1–2 mg/kg/day oral prednisone or equivalent upon improvement.
 
• Initiate hormone replacement if clinically indicated.
 
• If event resolves to Grade 1 or better, resume atezolizumab.b
 
• If event does not resolve to Grade 1 or better while withholding atezolizumab, permanently discontinue atezolizumab and contact Medical Monitor.c
 
• For recurrent hypophysitis, treat as a Grade 4 event.
 

Hypophysitis (pan-hypopituitarism), Grade 4	
 
• Permanently discontinue atezolizumab and contact Medical Monitor.c
 
• Refer patient to endocrinologist.
 
• Perform brain MRI (pituitary protocol).
 
• Initiate treatment with 1–2 mg/kg/day IV methylprednisolone or equivalent and convert to 1–2 mg/kg/day oral prednisone or equivalent upon improvement.
 
• Initiate hormone replacement if clinically indicated.
 

MRI=magnetic resonance imaging; TSH=thyroid-stimulating hormone.

a Atezolizumab may be withheld for a longer period of time (i.e., > 12 weeks after event onset) to allow for corticosteroids (if initiated) to be reduced to ≤ 10 mg/day oral prednisone or equivalent. The acceptable length of the extended period of time must be agreed upon by the investigator and the Medical Monitor.

b If corticosteroids have been initiated, they must be tapered over ≥ 1 month to ≤ 10 mg/day oral prednisone or equivalent before atezolizumab can be resumed.

c Resumption of atezolizumab may be considered in patients who are deriving benefit and have fully recovered from the immune-related event. Patients can be re-challenged with atezolizumab only after approval has been documented by both the investigator (or an appropriate delegate) and the Medical Monitor.

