### Risks Associated with Atezolizumab and Guidelines for Management of Adverse Events Associated with Atezolizumab (cont.)

**Table 3 Management Guidelines for Immune-Related Myocarditis**

Event	Management
Immune-related myocarditis, Grade 1	
 
• Refer patient to cardiologist.
 
• Initiate treatment as per institutional guidelines.
 

Immune-related myocarditis, Grade 2	
 
• Withhold atezolizumab for up to 12 weeks after event onset a and contact Medical Monitor.
 
• Refer patient to cardiologist.
 
• Initiate treatment as per institutional guidelines and consider antiarrhythmic drugs, temporary pacemaker, ECMO, or VAD as appropriate.
 
• Consider treatment with 1–2 mg/kg/day IV methylprednisolone or equivalent and convert to 1–2 mg/kg/day oral prednisone or equivalent upon improvement.
 
• If event resolves to Grade 1 or better, resume atezolizumab. b
 
• If event does not resolve to Grade 1 or better while withholding atezolizumab, permanently discontinue atezolizumab and contact Medical Monitor. c
 

Immune-related myocarditis, Grade 3–4	
 
• Permanently discontinue atezolizumab and contact Medical Monitor. c
 
• Refer patient to cardiologist.
 
• Initiate treatment as per institutional guidelines and consider antiarrhythmic drugs, temporary pacemaker, ECMO, or VAD as appropriate.
 
• Initiate treatment with 1–2 mg/kg/day IV methylprednisolone or equivalent and convert to 1–2 mg/kg/day oral prednisone or equivalent upon improvement.
 
• If event does not improve within 48 hours after initiating corticosteroids, consider adding an immunosuppressive agent.
 
• If event resolves to Grade 1 or better, taper corticosteroids over <math>\geq 1</math> month.
 

ECMO=extracorporeal membrane oxygenation; VAD=ventricular assist device.

a Atezolizumab may be withheld for a longer period of time (i.e., > 12 weeks after event onset) to allow for corticosteroids (if initiated) to be reduced to  $\leq 10$  mg/day oral prednisone or equivalent. The acceptable length of the extended period of time must be agreed upon by the investigator and the Medical Monitor.

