**Table 7 Management Guidelines for Immune-Related Meningoencephalitis**

Event	Management
Immune-related meningoencephalitis, all grades	
 
• Permanently discontinue atezolizumab and contact Medical Monitor. a
 
• Refer patient to neurologist.
 
• Initiate treatment with 1–2 mg/kg/day IV methylprednisolone or equivalent and convert to 1–2 mg/kg/day oral prednisone or equivalent upon improvement.
 
• If event does not improve within 48 hours after initiating corticosteroids, consider adding an immunosuppressive agent.
 
• If event resolves to Grade 1 or better, taper corticosteroids over ≥ 1 month.
 

a Resumption of atezolizumab may be considered in patients who are deriving benefit and have fully recovered from the immune-related event. Patients can be re-challenged with atezolizumab only after approval has been documented by both the investigator (or an appropriate delegate) and the Medical Monitor.

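### Table 5's catch-all row does not exempt events managed in Appendix 8, so for eight event types its default is to resume atezolizumab where Appendix 8's default is to stop, with rechallenge only on approval

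*Combined protocol and SAP*

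**What the plan says.** The event column of Table 5's last row reads "Grade 3 or 4 or intolerable Grade 2 treatment-related toxicities not described above and in" Table 4. The row withholds all study treatment. On atezolizumab it then says: "If event resolves to Grade 1 or better within 12 weeks, resume atezolizumab at fixed dose. If not, permanently discontinue atezolizumab". A separate bullet gives cobimetinib 28 days to recover and resumes it one dose level lower. Footnote c, marked at the end of the atezolizumab bullet, says: "Patients can be rechallenged with atezolizumab only after approval has been documented by both the investigator (or an appropriate delegate) and the Medical Monitor".

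For its part, Appendix 8 has eight management tables. For meningoencephalitis at all grades the instruction is "Permanently discontinue atezolizumab and contact Medical Monitor". For the thyroid it is "Permanently discontinue atezolizumab and contact Medical Monitor for life-threatening immune-related hyperthyroidism". Other rows give the same order for severe grades of other events. The opening section of Appendix 8 qualifies every such stop: atezolizumab may be resumed if the patient is benefiting, has fully recovered, and both the investigator and the Medical Monitor have documented approval.

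On how the two sources relate, Section 4.3.2.2 sends atezolizumab-associated events to Appendix 8. Section 5 says each drug has its own guidelines. Section 5.1.3.4 sends a list of named toxicities to Table 5 and atezolizumab-specific events to Appendix 8. No sentence says which prevails where both apply.

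**The concern.** A catch-all row takes in everything not carved out of it. This one carves out events with their own Table 5 row but not events whose only specific rule is in Appendix 8. A site working from Table 5 alone could treat a Grade 3 myocarditis that has settled to Grade 1 as a routine restart. Appendix 8 makes that case a stop, to be reversed only by a documented joint decision after full recovery. The recovery thresholds also differ, since Grade 1 is not full recovery. What is at stake is consistent safety management across about 20 centers, not any estimate.

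**Working it through.** No arithmetic on the trial's figures applies, so the check sets the two texts side by side.

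**Scope of the row.** Table 4 lists grades and cobimetinib doses, not events, and covers any Grade 3 or 4 toxicity. If being in Table 4 alone excluded an event, no Grade 3, Grade 4 or intolerable Grade 2 event would be left and the row would be empty. The workable reading is that the row applies to events with no Table 5 row of their own.

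**Count.** Ten Appendix 8 rows order an outright permanent stop. Two of them, infusion-related reactions and immune-related ocular events at Grade 3 or 4, have a Table 5 row that points to Appendix 8. That leaves 10 − 2 = 8:

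| Event type | Grades stopped | Appendix 8 table | Overlap with the catch-all row | Corticosteroids in Appendix 8 |
|---|---|---|---|---|
| Hyperthyroidism | life-threatening | 1 | all | none named |
| Hypophysitis | 4 | 1 | all | directed |
| Myocarditis | 3–4 | 3 | all | directed |
| Pancreatitis | 4 | 5 | all | directed |
| Neuropathy | 3–4 | 6 | all | institutional guidelines |
| Myasthenia gravis / Guillain-Barré | any | 6 | Grade 3–4 or intolerable Grade 2 | to be considered |
| Meningoencephalitis | all | 7 | Grade 3–4 or intolerable Grade 2 | directed |
| Renal event | 3–4 | 8 | all | directed |

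So 6 of the 8 overlap at every grade that Appendix 8 stops, and 2 only in part.

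**Recurrence rules.** Three more Appendix 8 stops apply on recurrence. The one for Grade 3–4 amylase or lipase elevation lies wholly within the row. Those for Grade 2–3 pancreatitis and hypophysitis ("For recurrent hypophysitis, treat as a Grade 4 event") overlap only at Grade 3 or intolerable Grade 2.

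**Opposite direction.** Appendix 8 continues atezolizumab for Grade 2 hyperglycemia and for Grade 2 amylase or lipase elevation. If such an event is treatment-related and judged intolerable, the catch-all row withholds it.

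**Pointers.** Of Appendix 8's eight tables, Table 5 points to 2 (infusion-related reactions, ocular), so 8 − 2 = 6 have no pointer.

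**How firm the Appendix 8 stop is.** Seven of the eight rows carry the rechallenge footnote. The renal row does not, but the opening section of Appendix 8 covers it. The stop is a default with an approved exception.

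**What Table 5 says about approval.** In the general-guidance row, the same benefit, full-recovery and joint-approval footnote (there lettered b) is attached to the sentence on resuming atezolizumab after corticosteroids for an atezolizumab-related toxicity. Appendix 8 directs corticosteroids for 5 of the 8 and says to consider them for 1 more. In the catch-all row, footnote c follows a pair of sentences, one on resuming and one on stopping. Usage elsewhere in Table 5 is mixed. For Grade 2 pneumonitis the approval footnote is on the discontinue bullet and not on the resume bullet. For raised transaminases with raised bilirubin it is on the restart bullet.

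**The case against.** The strongest reply is that the protocol already divides the work. Section 5.1.3.4 names the toxicities that Table 5 handles, none of the eight is among them, and atezolizumab-specific events go to Appendix 8. Sections 4.3.2.2 and 5 agree. Appendix 8 says outright that myocarditis, meningoencephalitis and nephritis are to be treated by its own tables, and a rule naming the event and grade ordinarily outranks a residual row. Section 4.6.1 requires permanent discontinuation for intolerable drug-related toxicity, or for any condition that makes continuing unsafe, whatever Table 5 says.

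Most of this stands, and it settles the intent. It does not remove the contradiction, because the row's wording still reaches these events and no sentence ranks the sources. Table 5 defers expressly to Appendix 8 in two rows, which makes its silence in the last row easier to misread.

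The footnotes also narrow the gap. When corticosteroids are given, the general-guidance row brings in joint approval before resumption. That leaves neuropathy and hyperthyroidism, for which Appendix 8 names no corticosteroid, dependent on how footnote c is read.

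A reader might infer that Appendix 8 bars atezolizumab absolutely after these events and that Table 5 overrides it. The documents do not support that: Appendix 8 itself permits rechallenge, and other text points to Appendix 8 as governing.

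**Conclusion.** Wrong as written, minor. For eight event types, at the grades the catch-all row covers, two stated rules set different defaults: resume at Grade 1 or better within 12 weeks, or stop with rechallenge only after benefit, full recovery and documented joint approval.

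This rests on reading the row as residual, on treating life-threatening hyperthyroidism as within Grade 4, and on the event being judged treatment-related. Confidence is high that the exemption is missing. It is lower about what any site would do, given the pointers and footnotes.

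Reporting is a further safeguard. Six of the eight types are on the list of adverse events of special interest in Section 5.2.3 and so are reportable within 24 hours. Myocarditis with a symptomatic LVEF decrease also meets an earlier Table 5 row that calls for Medical Monitor discussion before atezolizumab resumes. Reporting informs the sponsor but does not tell the investigator which rule to follow.

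The documents give no incidence for these events under the combination, so no patient count is claimed. No endpoint, estimate or sample size is affected.

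**What to change.** In the last row of Table 5:

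- Change the first bullet to: *Withhold cobimetinib. Withhold atezolizumab, except that for events listed in Appendix 8 tables, follow Appendix 8 for atezolizumab (withholding, resumption and discontinuation).*
- Limit the 12-week atezolizumab bullet to events not listed in those tables.
- Leave the 28-day cobimetinib bullet unchanged.

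Add one sentence to Section 5.1.3.4 stating that Appendix 8 governs atezolizumab for the events managed in its own tables. The pulmonary, hepatic, gastrointestinal and dermatologic classes, which Appendix 8 sends back to Section 5.1.3.4, have no table there and stay with Table 5.

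The first bullet has to change as well as the second. Otherwise the row would still withhold atezolizumab for intolerable Grade 2 hyperglycemia or amylase/lipase elevation, where Appendix 8 continues it. An exemption in the row's event column would be worse, because Appendix 8's tables direct atezolizumab only and the cobimetinib instructions for these events would be lost.

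The cost is two edited bullets and one sentence at the next amendment, with no change to data collection or analysis.

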## 5.2 SAFETY PARAMETERS AND DEFINITIONS

Safety assessments will consist of monitoring and recording adverse events, including serious adverse events and adverse events of special interest, performing protocol-specified safety laboratory assessments, measuring protocol-specified vital signs, and conducting other protocol-specified tests that are deemed critical to the safety evaluation of the study.

Certain types of events require immediate reporting to the Sponsor, as outlined in [Section 5.4](#).

### **5.2.1 Adverse Events**

According to the ICH guideline for Good Clinical Practice, an adverse event is any untoward medical occurrence in a clinical investigation subject administered a pharmaceutical product, regardless of causal attribution. An adverse event can therefore be any of the following:

- Any unfavorable and unintended sign (including an abnormal laboratory finding), symptom, or disease temporally associated with the use of a medicinal product, whether or not considered related to the medicinal product
- Any new disease or exacerbation of an existing disease (a worsening in the character, frequency, or severity of a known condition), except as described in Section [5.3.5.10](#)
- Recurrence of an intermittent medical condition (e.g., headache) not present at baseline
- Any deterioration in a laboratory value or other clinical test (e.g., ECG, X-ray) that is associated with symptoms or leads to a change in study treatment or concomitant treatment or discontinuation from study drug
- Adverse events that are related to a protocol-mandated intervention, including those that occur prior to assignment of study treatment (e.g., screening invasive procedures such as biopsies)

### **5.2.2 Serious Adverse Events (Immediately Reportable to the Sponsor)**

A serious adverse event is any adverse event that meets any of the following criteria:

- Is fatal (i.e., the adverse event actually causes or leads to death)
- Is life threatening (i.e., the adverse event, in the view of the investigator, places the patient at immediate risk of death)

This does not include any adverse event that, had it occurred in a more severe form or was allowed to continue, might have caused death.

- Requires or prolongs inpatient hospitalization (see Section [5.3.5.11](#))
- Results in persistent or significant disability/incapacity (i.e., the adverse event results in substantial disruption of the patient's ability to conduct normal life functions)
- Is a congenital anomaly/birth defect in a neonate/infant born to a mother exposed to study drug
- Is a significant medical event in the investigator's judgment (e.g., may jeopardize the patient or may require medical/surgical intervention to prevent one of the outcomes listed above)

The terms "severe" and "serious" are not synonymous. Severity refers to the intensity of an adverse event (e.g., rated as mild, moderate, or severe, or according to National Cancer Institute Common Terminology Criteria for Adverse Events, Version 4.0 [NCI CTCAE v4.0]; see Section 5.3.3); the event itself may be of relatively minor medical significance (such as severe headache without any further findings).

Severity and seriousness need to be independently assessed for each adverse event recorded on the eCRF.

Serious adverse events are required to be reported by the investigator to the Sponsor immediately (i.e., no more than 24 hours after learning of the event; see Section 5.4.2 for reporting instructions).

### **5.2.3 Adverse Events of Special Interest (Immediately Reportable to the Sponsor)**

Adverse events of special interest are required to be reported by the investigator to the Sponsor immediately (i.e., no more than 24 hours after learning of the event; see Section 5.4.2 for reporting instructions). Adverse events of special interest for this study are as follows:

- Severe hepatic events
  - Cases of potential drug-induced liver injury that include an elevated ALT or AST in combination with either an elevated bilirubin or clinical jaundice, as defined by Hy's law (see Section 5.3.5.7)
  - Hepatitis, including AST or ALT > 10 × ULN
- Suspected transmission of an infectious agent by the study drug, as defined below:
  - Any organism, virus, or infectious particle (e.g., prion protein transmitting transmissible spongiform encephalopathy), pathogenic or non-pathogenic, is considered an infectious agent. A transmission of an infectious agent may be suspected from clinical symptoms or laboratory findings that indicate an infection in a patient exposed to a medicinal product. This term applies only when a contamination of the study drug is suspected.
- Pneumonitis
- Endocrinopathies: diabetes mellitus, pancreatitis, adrenal insufficiency, hypothyroidism or hyperthyroidism
- Systemic lupus erythematosus
- Neurological disorders: Guillain-Barré syndrome, myasthenic syndrome, myasthenia gravis, and meningoencephalitis
- Nephritis
- Events suggestive of hypersensitivity, infusion-related reactions, cytokine-release syndrome, influenza-like illness, systemic inflammatory response syndrome, or systemic immune activation

- Ocular toxicities
  - Uveitis or retinitis
  - Serous retinopathy, including events of retinal detachment, retinal pigment epithelium detachment, neurosensory retinal detachment, and central serous chorioretinopathy
  - Retinal vein occlusion
- Myositis
- Cardiac disorders
  - Grade  $\geq$  2 atrial fibrillation, myocarditis, or pericarditis
  - Symptomatic heart failure or Grade  $\geq$  3 LVEF reduction
- Vasculitis
- Rhabdomyolysis, Grade  $\geq$  3 CPK elevation, or myopathies
- Grade  $\geq$  3 hemorrhage or any grade cerebral hemorrhage
- Grade  $\geq$  3 rash
- Grade  $\geq$  3 diarrhea
- Colitis

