### **5.1.2 Risks Associated with Atezolizumab**

Atezolizumab has been associated with risks such as IRRs and immune-related hepatitis, pneumonitis, colitis, pancreatitis, diabetes mellitus, hypothyroidism, hyperthyroidism, adrenal insufficiency, hypophysitis, Guillain-Barré syndrome, myasthenic syndrome or myasthenia gravis, meningoencephalitis, myocarditis, and *nephritis*. In addition, systemic immune activation is a potential risk associated with atezolizumab. Refer to Section 6 of the Atezolizumab Investigator's Brochure for a detailed description of anticipated safety risks for atezolizumab.

Systemic immune activation is a rare condition characterized by an excessive immune response. Given the mechanism of action of atezolizumab, systemic immune activation is a potential risk when administered in combination with other immunomodulating agents. Systemic immune activation should be included in the differential diagnosis for patients who, in the absence of an alternative etiology, develop a sepsis-like syndrome after administration of atezolizumab, and the initial evaluation should include the following:

- CBC with peripheral smear
- PT, PTT, fibrinogen, and D-dimer
- Ferritin
- Triglycerides
- AST, ALT, and total bilirubin
- LDH
- Complete neurologic and abdominal examination (assess for hepatosplenomegaly)

If systemic immune activation is still suspected after the initial evaluation, contact the Medical Monitor for additional recommendations.

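### Hypophysitis is the only atezolizumab-associated risk named in Section 5.1.2 with no entry in the Section 5.2.3 list of adverse events of special interest

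*Combined protocol and SAP*

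**What the plan says.** Section 5.1.2 lists the risks in one sentence. It opens with "Atezolizumab has been associated with risks such as IRRs and immune-related hepatitis, pneumonitis, colitis, pancreatitis, diabetes mellitus", continues with "hypothyroidism, hyperthyroidism, adrenal insufficiency, hypophysitis, Guillain-Barré syndrome, myasthenic syndrome or myasthenia gravis, meningoencephalitis, myocarditis" and ends with nephritis. It then adds that "systemic immune activation is a potential risk associated with atezolizumab".

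Section 5.2.3 introduces its list with "Adverse events of special interest for this study are as follows". The endocrine line is "Endocrinopathies: diabetes mellitus, pancreatitis, adrenal insufficiency, hypothyroidism or hyperthyroidism".

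Appendix 8 names pituitary disorders among the endocrine events associated with atezolizumab. Its Table 1 has one row for Grade 2 or 3 hypophysitis, where atezolizumab is withheld, and one for Grade 4, where it is permanently discontinued. It also says "For recurrent hypophysitis, treat as a Grade 4 event".

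AESI status has these consequences:
- Section 5.4 limits the 24-hour duty to serious adverse events, AESIs, pregnancies, and overdose, medication error, abuse or misuse.
- Section 5.7 commits the sponsor to prompt evaluation of serious adverse events and AESIs against cumulative product experience.
- Section 5.5.2 provides for sponsor follow-up of serious adverse events, AESIs and pregnancies.
- Section 6.5 reports incidence, percentages and exposure-adjusted rates by cohort for several categories, AESIs being one.

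**The concern.** The protocol treats hypophysitis as a distinct, recognised atezolizumab event, but the list that triggers expedited handling omits it and gives no reason. The endocrine line is a closed list of five terms, with nothing to show that they are only examples.

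The reporting burden comes out uneven within one organ class. Asymptomatic hypothyroidism, for which Appendix 8 continues atezolizumab, is an AESI with a 24-hour clock. Grade 2 or 3 hypophysitis, for which Appendix 8 withholds atezolizumab, is not on that clock unless the case is also serious. At stake are the speed and completeness with which one known immune-related event reaches the sponsor, and whether it counts in the AESI summary.

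**Working it through.** No calculated figure is involved. The check is a term-by-term comparison of two lists, followed by tracing what happens to a case.

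**Step 1. Compare the lists.** Myasthenic syndrome and myasthenia gravis are counted as one risk, because Section 5.1.2 joins them.

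| Risk in Section 5.1.2 | Entry in Section 5.2.3 |
|---|---|
| Infusion-related reactions | Yes, hypersensitivity and infusion line |
| Hepatitis | Yes: "Hepatitis, including AST or ALT > 10 × ULN" |
| Pneumonitis | Yes |
| Colitis | Yes |
| Pancreatitis | Yes, endocrine line |
| Diabetes mellitus | Yes, endocrine line |
| Hypothyroidism | Yes, endocrine line |
| Hyperthyroidism | Yes, endocrine line |
| Adrenal insufficiency | Yes, endocrine line |
| **Hypophysitis** | **None** |
| Guillain-Barré syndrome | Yes, neurological line |
| Myasthenic syndrome or myasthenia gravis | Yes, neurological line |
| Meningoencephalitis | Yes, neurological line |
| Myocarditis | Yes, but the line opens with a Grade 2 or higher qualifier |
| Nephritis | Yes |

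Associated risks: 15 named, 14 matched, 15 − 14 = 1 unmatched. With the potential risk of systemic immune activation, which does have an entry, the count is 16 named, 15 matched, 1 unmatched.

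**Step 2. Can another AESI term catch the case?** Sometimes. Adrenal insufficiency and hypothyroidism are AESI terms and could be recorded first. But Section 5.3.5.2 asks for the diagnosis rather than its signs and symptoms, and has earlier entries replaced once a diagnosis is made. Section 5.3.5.3 asks that secondary events generally be identified by their primary cause unless severe or serious. Both rules push the record towards hypophysitis, the term without an entry.

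**Step 3. Follow a case recorded as hypophysitis.**

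| Route | Not serious | Serious |
|---|---|---|
| 24-hour report (Section 5.4) | No | Yes |
| Prompt sponsor evaluation (Section 5.7) | No | Yes |
| AESI summary (Section 6.5) | No | No |
| Overall adverse event tables (Section 6.5) | Yes | Yes |
| Grade 3 or higher summary | If Grade 3 or higher | If Grade 3 or higher |
| Interruption or discontinuation summary | If drug withheld or stopped | If drug withheld or stopped |

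A serious case reaches the sponsor on time but still does not count as an AESI. A Grade 1 case has no management row in Appendix 8, so if it is not serious and treatment continues, it appears only in the overall tables.

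**The case against.** The strongest reply is that little is lost. Section 5.3.1 puts every adverse event on the eCRF, and Section 3.1.2 has the study team review adverse events on an ongoing basis. Appendix 8 has atezolizumab withheld or stopped for Grade 2 to 4 hypophysitis, so each such case managed as written enters the interruption or discontinuation summary, which carries the same incidence and exposure-adjusted rates. Appendix 8 also requires Medical Monitor contact for Grade 4 events and for Grade 2 or 3 events that do not resolve while drug is withheld. An investigator may judge a case a significant medical event, which makes it serious. All of this stands, and it rules out several stronger readings that a reader might draw:

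- *That an immune-related endocrine rate will be understated.* Section 6.5 plans no such rate. The AESI category also includes rash, diarrhea, hemorrhage and CPK elevation, and the count under the mapped term is unaffected.
- *That the sponsor's ongoing review will see cases late.* That review is not confined to serious events and AESIs. What is lost is the 24-hour clock for some cases.
- *That every non-serious case is missed.* Some may be reported as adrenal insufficiency or hypothyroidism.
- *That nothing else in Section 5.1.2 can escape.* Grade 1 myocarditis may fall outside its line, depending on how far the grade qualifier reaches. Myocarditis is at least listed, so hypophysitis remains the only risk with no entry at all.

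It can also be said that the Section 5.1.2 list is illustrative, that it defers to the Investigator's Brochure, and that nothing obliges the two lists to match; Section 5.2.3 includes lupus, myositis and vasculitis, which Section 5.1.2 does not name. That is fair, and the omission is not a formal contradiction. But an illustrative risk list does not explain why one risk it does name is left off the reporting list.

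**Conclusion.** The point holds as a narrow gap in safety reporting. One of 15 named atezolizumab-associated risks has no AESI entry. Non-serious cases recorded as hypophysitis fall outside the 24-hour duty and the prompt evaluation in Section 5.7, and all cases recorded under that term fall outside the AESI summary. The general adverse event data are intact, and the efficacy analyses are not touched.

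This rests on three assumptions: that the endocrine line is read as the closed list it appears to be, that AESI in Section 6.5 means the Section 5.2.3 list (no other definition is given), and that sites record the diagnosis as Section 5.3.5.2 asks. One in 15 counts list terms, not patients. The documents give no hypophysitis frequency, so the number of affected cases cannot be estimated. This is a cheap improvement, not a threat to the trial's conclusions.

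**What to change.** Add hypophysitis to the endocrinopathies line of Section 5.2.3, so that it agrees with Section 5.1.2 and Appendix 8. If the omission is deliberate, state the reason there instead. While that section is open, make clear whether the Grade 2 or higher qualifier applies to myocarditis.

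No treatment rule changes, and Section 6.5 needs no edit because it takes AESIs as a category. Version 4 has already revised Section 5.1.2 and Appendix 8 to add nephritis, so this belongs with the same upkeep. The cost is one added term in an amendment and some additional 24-hour reports, a number that the documents do not allow to be estimated.
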